2.4 Rationale for choice of combination drugs

Not Applicable.

2.5 Rationale for choice of comparators drugs

Not applicable.

2.6 Risks and benefits

The primary clinical risks with ruxolitinib treatment are the potential consequences of decreased hematopoietic proliferation secondary to the inhibition of growth factor pathways associated with JAK2 inhibition. Dose-dependent, reversible thrombocytopenia has been observed in patients with MF and represents the DLT. Anemia and, less frequently, neutropenia have also been observed in patients with MF treated with ruxolitinib. Increased rates of infection and anemia are potential risks of myelosuppression, and there are other consequences of anemia including the burden and risks of transfusion.

Of note, the dosing approach proposed in this study may decrease the risk of patients developing cytopenias compared to the standard dose approach utilized in the two phase III pivotal studies.

A dose escalation starting at week 12 aims to achieve a maintenance dose for each patient that maximizes the benefits from ruxolitinib while keeping the treatment well tolerated. The main potential benefit of the proposed dosing approach in the study resides in achieving similar levels of efficacy seen in previous clinical trial experiences with an improved safety and tolerability profile expressed by lower rates of cytopenias and transfusion requirements.

Appropriate eligibility criteria, as well as specific dose modification and stopping rules, are included in this protocol. The risk to patients in this trial may be minimized by compliance with the eligibility criteria and study procedures, as well as and close clinical monitoring. There may be unforeseen risks with ruxolitinib which could be serious. Please refer to the latest [Investigator Brochure].

3 Objectives and endpoints

Objectives and related endpoints are described in [Table 3-1](#) below.

[figure not shown]
[figure not shown]
[figure not shown]

Table 3-1 Objectives and related endpoints

Objective	Endpoint	Analysis
Primary		
To determine the spleen length response rate at week 24.	Proportion of patients achieving a 50% reduction in spleen length at week 24.	Refer to Section 10.4
Secondary		
To evaluate safety.	Safety will be assessed by 
 • Frequency and severity of adverse events and serious adverse events and AEs leading to discontinuations. • Changes in hematology/biochemistry parameters over time. 	Refer to Section 10.5.1
To determine the spleen length response rate at week 48.	Proportion of patients achieving a 50% reduction in spleen length at week 48.	
To evaluate the effect of ruxolitinib on spleen length.	Percent change from baseline in spleen length over time.	
To evaluate the effect of ruxolitinib on symptoms.	Summary of the Modified MFSAF v2.0 and MF-7 over time.	
To evaluate the effect of ruxolitinib on Patient Global Impression of Change (PGIC).	PGIC at each visit where measured.	
To evaluate the effect of ruxolitinib on transfusion requirements.	Summary of transfusions over time. For Transfusion Dependent (TD)* patients, the following will be analyzed: 
 • Transfusion independence (TI) rate (requiring no transfusion for ≥12 weeks at any time). • Transfusion response rate (not TD: having 5 or less transfusion for ≥12 weeks at any time). 	

[figure not shown]
related parameters
and serum iron.

[figure not shown]
[figure not shown]
Novartis
Oncology Clinical Trial Protocol (v00)

Confidential

Page 34

3 Protocol No.

4 Study design

4.1 Description of study design

This is a multicenter phase II, open label, single arm study to assess the efficacy and safety of ruxolitinib in patients with Primary Myelofibrosis (PMF), Post-Polycythemia Vera-Myelofibrosis (PPV-MF), or Post-Essential Thrombocythemia Myelofibrosis (PET-MF) who have splenomegaly that is equal to or greater than 5 cm below the left costal margin and with anemia defined by Hb less than 10 g/dL.

The target number of patients for this trial is 50.

Screening

Screening evaluations should be performed to determine the eligibility for the study and establish a baseline prior to dosing, and should be conducted between Day -28 and Day -1. However platelet and hemoglobin counts should be performed within a maximum of 7 days from the first dose of ruxolitinib. See [Section 7](#) for complete screening and assessment details.

Treatment Period

All patients who consent to study participation will start treatment with ruxolitinib upon meeting all study eligibility criteria and none of the exclusion criteria. The treatment period commences on Day 1 (day of first dose of study drug). Patients will have study visits at Day 1 and at Weeks 4, 8, 12, 16, 20, 24, and every 12 weeks thereafter.

Patients will be treated with ruxolitinib 10 mg BID for the first 12 weeks and up titrations thereafter. See [Section 6.1.1](#) for details.

[figure not shown]
Patients will receive treatment on this trial as long as they benefit from it until 48 weeks after Last Patient First Treatment date.

End of Study Treatment (EoT)

Patients may be discontinued from treatment with the study drug earlier due to unacceptable toxicity, disease progression and/or at the discretion of the investigator or the patient.

Patients who in the opinion of the investigator are still deriving clinical benefit from ruxolitinib may continue treatment with commercial ruxolitinib according to local regulations in countries with commercially available ruxolitinib.

Should ruxolitinib not be available to patients commercially after the end of treatment visit, every effort will be made to continue provision of ruxolitinib off study. Novartis will have a transition plan in place to ensure that patients have access to ruxolitinib without delays to treatment.

Safety Follow up period

The safety follow up period is 30 days after the last dose of study treatment. All patients must have safety evaluations for 30 days, after the last dose of study treatment. Data collected should be added to the Adverse Events CRF and the Concomitant Medications CRF.

4.2 Timing of interim analyses and design adaptations

Not applicable.

4.3 Definition of end of study

The end of the study (last patient last visit) will occur after completion of the last follow up visit of the last patient on treatment with ruxolitinib.

Patients who in the opinion of the investigator are still deriving clinical benefit from ruxolitinib may continue treatment with commercial ruxolitinib according to local regulations in countries with commercially available ruxolitinib.

Should ruxolitinib not be available to patients commercially after the end of treatment visit, every effort will be made to continue provision of ruxolitinib off study. Novartis will have a transition plan in place to ensure that patients have access to ruxolitinib without delays to treatment.

4.4 Early study termination

The study can be terminated at any time for any reason by Novartis. Should this be necessary, the patient should be seen as soon as possible and the same assessments should be performed as described in [Section 7](#) for a discontinued or withdrawn patient. The investigator may be informed of additional procedures to be followed in order to ensure that adequate consideration is given to the protection of the patient's interests. The investigator will be responsible for informing IRBs and/or ECs of the early termination of the trial.

5 Population

5.1 Patient population

[figure not shown]
Adult Primary Myelofibrosis (PMF), Post-Polycythemia Vera-Myelofibrosis (PPV-MF), or Post-Essential Thrombocythemia Myelofibrosis (PET-MF) patients with splenomegaly at baseline that is equal to or greater than 5 cm below the left costal margin and with anemia at baseline defined by Hb less than 10 g/dL will be eligible to participate in this trial.

Patients enrolled in this study are not permitted to participate in additional parallel investigational drug or device studies.

The investigator or designee must ensure that only patients who meet all the following inclusion and none of the exclusion criteria are offered treatment in the study.

5.2 Inclusion criteria

Patients eligible for inclusion in this study have to meet **all** of the following criteria:

Written informed consent must be obtained prior to any screening procedures.

1. Male or female patients aged ≥ 18 years of age.
2. Patients must be diagnosed with PMF, according to the 2016 revised International Standard Criteria (Arber et al. 2016), PPV MF or PET-MF (Barosi 2008), irrespective of JAK2 mutation status.
3. Patients with palpable splenomegaly that is equal to or greater than 5 cm below the left costal margin.
4. Patients with a hemoglobin less than 10 g/dL
5. Patients with a history of transfusions must have a documented transfusion record in the previous 12 weeks to baseline.
6. Patients with an ECOG performance status of 0, 1, or 2.
7. Patients with a peripheral blood blast percentage count of $< 10\%$.
8. Patients must have recovered or stabilized sufficiently from any adverse drug reactions associated with prior treatments before beginning treatment with ruxolitinib.

5.3 Exclusion criteria

Patients eligible for this study must not meet **any** of the following criteria:

1. Patients with prior treatment with any JAK1 or JAK2 inhibitor.
2. Patients with known hypersensitivity to ruxolitinib or other JAK1/JAK2 inhibitors, or to their excipients.
3. Patients eligible for hematopoietic stem cell transplantation (suitable candidate and a suitable donor is available).
4. Patients with inadequate bone marrow reserve at baseline as demonstrated by at least one of the following:
 - a. ANC that is $\leq 1,000/\mu\text{L}$.
 - b. Platelet count that is $< 50,000/\mu\text{L}$ without the assistance of growth factors, thrombopoietic factors or platelet transfusions.
 - c. Hemoglobin count that is ≤ 6.5 g/dL despite transfusions.
5. Patients with severely impaired renal function defined by:
Creatinine clearance less than 30 mL/min.
6. Patients with inadequate liver function defined by any of these:
 - a. Total bilirubin ≥ 2.5 x ULN and subsequent determination of direct bilirubin ≥ 2.5 x ULN;
 - b. Alanine aminotransferase (ALT) > 2.5 x ULN;
 - c. Aspartate aminotransferase (AST) > 2.5 x ULN.
7. Patients being treated concurrently with a strong (potent) systemic inhibitor or inducer of CYP3A4 at the time of Screening.
8. Presence of active bacterial, fungal, parasitic, or viral infection which requires therapy.
9. Known history of human immunodeficiency virus (HIV) infection or other immunodeficiency syndromes such as X-linked agammaglobulinemia and common variable immune deficiency.

10. Acute viral hepatitis or active chronic hepatitis B or C infection. Patients with *inactive* chronic infection (without viral replication) can be enrolled (See [Section 7.2.2.7](#))
11. History of progressive multifocal leuko-encephalopathy (PML).
12. Impairment of gastrointestinal (GI) function or GI disease that may significantly alter the absorption of ruxolitinib (e.g., ulcerative diseases, uncontrolled nausea, vomiting, diarrhea, malabsorption syndrome, small bowel resection).
13. History or current diagnosis of uncontrolled or significant cardiac disease, including any of the following:
 - a. Myocardial infarction within last 6 months
 - b. Uncontrolled congestive heart failure
 - c. Unstable angina within last 6 months
 - d. Clinically significant (symptomatic) cardiac arrhythmias (e.g. bradyarrhythmias, sustained ventricular tachycardia, and clinically significant second or third degree AV block without a pacemaker)
14. Significant concurrent, uncontrolled medical condition which, in the investigator's opinion, would jeopardize the safety of the patient or compliance with the protocol.
15. Patients undergoing treatment with another investigational medication or having been treated with an investigational medication within 30 days or 5 half-lives (whichever is longer) prior to the first dose of study drug.
16. Patients with a history of malignancy in the past 3 years, except for treated early stage squamous or basal cell carcinoma.
17. Patients who are unable to comprehend or are unwilling to sign an ICF.
18. Pregnant or nursing (lactating) women
19. Women of child-bearing potential, defined as all women physiologically capable of becoming pregnant, unless they are using highly effective methods of contraception throughout the study duration inclusive of 30 day safety follow up. Highly effective contraception methods include:
 - a. Total abstinence (when this is in line with the preferred and usual lifestyle of the patient). Periodic abstinence (e.g., calendar, ovulation, symptothermal, post-ovulation methods) and withdrawal are not acceptable methods of contraception
 - b. Female sterilization (have had surgical bilateral oophorectomy with or without hysterectomy), total hysterectomy or tubal ligation at least six weeks before taking study treatment. In case of oophorectomy alone, only when the reproductive status of the woman has been confirmed by follow up hormone level assessment
 - c. Male sterilization (at least 6 months prior to screening). The vasectomized male partner should be the sole partner for that patient.
 - d. Use of oral, injected or implanted hormonal methods of contraception or placement of an intrauterine device (IUD) or intrauterine system (IUS) or other forms of hormonal contraception that have comparable efficacy (failure rate <1%), for example hormone vaginal ring or transdermal hormone contraception (in case of oral contraception you should have been using the same pill on a stable dose for a minimum of 3 months before screening)

Women are considered post-menopausal and not of child bearing potential if they have had 12 months of natural (spontaneous) amenorrhea with an appropriate clinical profile (e.g. age appropriate, history of vasomotor symptoms) or have had surgical bilateral oophorectomy (with or without hysterectomy), total hysterectomy or tubal ligation at least six weeks ago. In the case of oophorectomy alone, only when the reproductive status of the woman has been confirmed by follow up hormone level assessment is she considered not of child bearing potential.

6 Treatment

6.1 Study treatment

INC424 (ruxolitinib) tablets will be the only investigational drug in this study.

6.1.1 Dosing regimen

Table 6-1 Dose and treatment schedule

Study treatments	Pharmaceutical form and route of administration	Dose	Frequency and/or Regimen
INC424/ruxolitinib	5mg Tablet for oral use	Starting dose 10 mg bid (2 tablets of INC424 5mg, approximately 12 hours apart: morning and night), to be increased or decreased per standardized dosing paradigm and not to exceed 25 mg bid.	Twice Daily (BID), unless instructed to temporarily withhold dosing for safety

INC424 (ruxolitinib) 10 mg BID (2 tablets of INC424 5mg) will be self-administered as starting dose for treatment of anemic MF patients. This dose will be maintained for the first 12 weeks and titrated up thereafter unless they have met criteria for dose hold or dose reduction.

Ruxolitinib should be taken orally, approximately 12 hours apart (morning and night) without regards to food. Ruxolitinib will be self-administered by the patient in an outpatient setting, and each investigator should instruct the patient to take the study drug as per protocol. All dosages prescribed and dispensed to the patient and all dose changes during the study must be recorded on the appropriate case report form (CRF).

6.1.2 Ancillary treatments

Not applicable.

6.1.3 Rescue medication

Not applicable.

6.1.4 Guidelines for continuation of treatment

See [Section 6.3](#)

6.1.5 Treatment duration

The planned minimum duration of treatment is 48 weeks. Patients may be discontinued from treatment with the study drug earlier due to unacceptable toxicity, disease progression and/or treatment is discontinued at the discretion of the investigator or the patient.

6.2 Dose escalation guidelines

6.2.1 Starting dose rationale

Phase I/II trials evaluated a number of different doses and schedules of ruxolitinib. Based on these, two phase III trials evaluated the efficacy and safety of ruxolitinib versus placebo in COMFORT I and versus BAT in COMFORT II in a population of patients with primary and secondary MF. In both phase III trials a starting dose of 20 mg orally BID was administered for patients with platelet counts from 200,000/ μL and a lower starting dose of 15 mg orally BID in patients with baseline platelet counts from 100,000 to 200,000/ μL .

Additional studies generated clinical data on the efficacy and tolerability of ruxolitinib in patients with MF and platelet counts from 50,000 to 100,000/ μL . A starting dose of 5 mg BID with subsequent optional up titrations every 4 weeks by dose increments of 5 mg OD was evaluated in a phase II open label single arm study INCB18424-258 in a population of patients with platelet counts from 50,000 to 100,000/ μL . Similarly, an expanded access program and phase IIIb study CINC424A2401 that recruited more than 2200 patients allowed the inclusion of patients with low platelet counts (50,000 to 100,000/ μL) to be treated with a 5 mg BID starting dose.

Furthermore, a Phase Ib study (EXPAND) evaluating the safety and MTD of ruxolitinib in patients with lower baseline platelet counts (50,000– 100,000/ μL) suggests that higher doses of ruxolitinib can be safely administered to patients with lower baseline platelet count. The maximum safe starting dose in this ongoing study was reported to be 15 mg BID for patients with platelet counts from 75,000 to 100,000/ μL and 10 mg BID for patients with platelet counts from 50,000 to 75,000/ μL .

Anemia may be ameliorated by lowering the dose of ruxolitinib or by concomitant use of erythropoietin stimulating agents and/or anabolic steroids (Reilly 2014). This approach may make particular sense in patients with anemia at the moment of treatment initiation with ruxolitinib in order to avoid further hemoglobin decrease, the need of blood transfusions or have them more frequently in patients already receiving regular transfusions for anemia.

An alternative strategy to start patients at 10 mg BID and titrate the dose up according to tolerability and response (Cervantes 2014, Harrison 2013) has anecdotally suggested improved tolerance and reduced adverse events yielding fewer treatment discontinuations and has been already included in treatment guidelines (Ho 2015, Reilly 2014).

Based on the above, a starting dose of 10 mg BID will be assigned to patients recruited in this phase II open label single arm study followed by gradual up titrations starting at week 12, based on efficacy and safety at the different evaluation visits. This approach assumes that starting at a lower dose may impact the rate of the initial hemoglobin decline and the nadir, by decreasing the level of JAK-mediated inhibition of hematopoiesis.

6.2.2 Provisional dose levels

[figure not shown]
Not Applicable.

6.2.3 Guidelines for dose escalations

Dose up titrations will be based on efficacy and platelet counts provided that ANC is $>500 \mu\text{L}$ and Hb level is $\geq 6.5 \text{ g/dL}$ as follows:

- A dose of 15 mg BID should be targeted in patients with platelet count $\geq 100 \times 10^9/\text{L}$ and $\leq 200 \times 10^9/\text{L}$ from week 12. This dose increase is optional for patients that achieved a $\geq 50\%$ reduction in spleen length at this visit relative to Baseline.
- A dose of 20 mg BID should be targeted in patients with platelet count $\geq 200 \times 10^9/\text{L}$ from week 16. This dose increase is optional for patients that achieved a $\geq 50\%$ reduction in spleen length at this visit relative to Baseline.
- Maximum dose allowed in the study is 25 mg BID and may be used from Week 20 in patients that did not achieve a 50% reduction in spleen length relative to Baseline and provided that platelet count is $\geq 200 \times 10^9/\text{L}$ at this visit.
- Patients who did not qualify for a dose increase at Week 12, may qualify for an increase at week 16 (from 10 mg BID to 15 mg BID). In that case, the Week 12 dose increase rules will apply. Similarly, patients who did not qualify for a dose increase at Week 16, may qualify for an increase later (from 15 mg BID to 20 mg BID). In that case, the Week 16 dose increase rules will apply.

Figure 6-1 Dosing Up-titration Diagram

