Considering the typical hemoglobin level for many MF patients is already at the Grade 0/Grade 1 border (hemoglobin of 10 g/dL), assessment of a dose regimen that might provide clinically meaningful symptomatic and spleen size reduction benefits of ruxolitinib while lessening the degree of worsening hemoglobin levels is warranted.

Current label recommendation on starting doses in MF are 5, 15 or 20 mg BID, depending on platelet counts $50-100 \times 10^9/L$, $100-200 \times 10^9/L$ or $>200 \times 10^9/L$ respectively, regardless of hemoglobin level at baseline.

There is increasing literature suggesting the use of lower starting doses with up titrations depending on safety and efficacy in patients with anemia ([Tabarroki 2013](#), [Cervantes 2014](#), [Reilly 2014](#), [Harrison 2013](#), [Ho 2015](#)).

This multicenter phase II open label single arm study proposes to prospectively evaluate a starting dose of ruxolitinib 10 mg BID for 12 weeks with subsequent up titrations of 15mg BID and 20 mg BID in anemic myelofibrosis patients defined as a baseline hemoglobin < 10 g/dL (Please see [Figure 6-1](#) for details). The trial will evaluate if this alternative dosing approach achieves spleen reduction and symptom improvement to levels consistent with those reported in previous clinical trials but with an improved tolerability assessed by incidence of adverse events and transfusion requirements.

[figure not shown]
[figure not shown]

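### Protocol 6.2.3 gives no written route to 15 mg BID for a patient whose platelets stay above 200 x 10^9/L; read literally, the dose stays at 10 mg BID to Week 16 and then doubles in one step

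*Protocol*

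**What the plan says.** Protocol 6.2.3 bases dose increases on spleen response and platelet count, provided ANC and hemoglobin are adequate.

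- First bullet: "15 mg BID should be targeted in patients with platelet count $\geq 100 \times 10^9/\text{L}$ and $\leq 200 \times 10^9/\text{L}$ from week 12".
- Second bullet: "A dose of 20 mg BID should be targeted in patients with platelet count" of at least 200 x 10^9/L, from Week 16. It names no dose that the patient must already be on.
- Third bullet: 25 mg BID may be used from Week 20 in patients at 200 x 10^9/L or more who have not reached a 50% spleen reduction.
- Fourth bullet: a patient who missed the Week 12 increase "may qualify for an increase at week 16 (from 10 mg BID to 15 mg BID). In that case, the Week 12 dose increase rules" govern again. A patient who missed the Week 16 increase "may qualify for an increase later (from 15 mg BID to 20 mg BID"), under the Week 16 rules.

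The first two increases are optional for a patient whose spleen length is already down by at least half.

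Elsewhere the regimen is described as stepwise. Section 2.1 gives "10 mg BID for 12 weeks with subsequent up titrations of 15mg BID and 20 mg BID". Section 6.2.1 says the starting dose is "followed by gradual up titrations starting at week 12". The product information in Appendix 6 (its section 4.2) limits an increase for insufficient efficacy to 5 mg twice daily.

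**The concern.** The first bullet admits platelets from 100 to 200 x 10^9/L and no higher. The fourth bullet's Week 16 catch-up applies the Week 12 rule again, so it keeps the same ceiling. A patient who stays above 200 therefore fails the 15 mg BID rule at Week 12 and again at Week 16, while the second bullet targets 20 mg BID from Week 16.

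The titration schedule is the intervention this trial sets out to test, in anemic patients for whom a gentle increase is the rationale. For this platelet group the written rules give a later first increase and then a doubling of the dose. Patients with lower counts move up earlier and by a smaller step.

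**Working it through.** The plan states no dose-exposure figure to reproduce, so the check traces the written rules and then does simple arithmetic.

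**Inputs (Protocol 6.2.3).** Starting dose 10 mg BID; 15 mg BID from Week 12 at 100 to 200 x 10^9/L; 20 mg BID from Week 16 at 200 x 10^9/L or more; Week 16 catch-up under the Week 12 rule.

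**Assumptions.** Platelets constant, ANC and hemoglobin adequate, no 50% spleen reduction, every targeted increase taken, and 25 mg BID not used.

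**Step 1: trace the first two bullets as written (mg BID).**

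| Platelets (x 10^9/L) | Weeks 12-16 | Weeks 16-20 | Weeks 20-24 |
|---|---|---|---|
| 80 | 10 | 10 | 10 |
| 150 | 15 | 15 | 15 |
| 200 | 15 | 20 | 20 |
| 201 or 300 | 10 | 20 | 20 |

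A count of exactly 200 falls in both platelet ranges and gives the described 10-15-20 sequence. A count of 201 does not.

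**Step 2: Weeks 12-16.** Above 200: 2 x 10 = 20 mg/day. At 100-200: 2 x 15 = 30 mg/day. Difference: 20/30 - 1 = -33%.

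**Step 3: mean daily dose over Weeks 12-24 (three 4-week blocks).**

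- Described titration, 15 then 20 mg BID: (30 + 40 + 40)/3 = 36.7 mg/day.
- Rules as written, above 200: (20 + 40 + 40)/3 = 33.3 mg/day.
- Ratio: 33.3/36.7 - 1 = -9%.
- For reference, a patient at 100-200 throughout: (30 + 30 + 30)/3 = 30.0 mg/day.

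The two paths for a patient above 200 differ only in Weeks 12-16, so the whole gap is 10/3 = 3.3 mg/day.

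**Step 4: size of the step.** At Week 16 the written rules move this patient from 10 to 20 mg BID. That increment of 10 mg BID is twice the maximum in the appended product information.

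**Step 5: test the correction.** With the upper limit removed from the Week 12 rule, a patient at 201 or 300 goes 10-15-20. The paths at 80, 150 and 200 do not change.

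**The case against.** **Figure 6-1.** Section 2.1 refers the reader to the up-titration diagram, which is not visible in this copy and may show the intended path. That is a reason to check it first. It does not remove the point: a figure giving 15 mg BID above 200 would contradict the first bullet's written limit, and the text would still need correcting.

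**A soft reading of the targets.** The section is headed as guidance. It can be argued that 15 and 20 mg BID are destination doses by platelet band, with 15 mg BID as a transit step for patients above 200. The fourth bullet's 15 to 20 mg BID step, the gradual titration in 6.2.1 and the label increment all favor this as the intent. But the fourth bullet treats the platelet ranges as conditions that a patient meets or fails, which makes the upper limit operative. The soft reading probably recovers what was meant; it is not what is written.

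**A stronger reading to avoid.** A reader might infer that the fourth bullet's 15 to 20 mg BID wording blocks the 20 mg BID step, leaving a patient above 200 at 10 mg BID throughout (20.0 mg/day over Weeks 12-24, 20.0/36.7 - 1 = -45%). The documents do not support this. The second bullet sets no prior-dose condition, and the fourth bullet's clause covers only patients who did not qualify at Week 16. A patient above 200 does qualify then.

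**Section 6.1.1.** A reader might also see a conflict with the statement that 10 mg BID is "maintained for the first 12 weeks and titrated up thereafter unless they have met criteria for dose hold or dose reduction". An increase at Week 16 is still after the first 12 weeks, so there is none.

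**Label bands.** Section 2.1 notes "Current label recommendation on starting doses in MF are 5, 15 or 20 mg BID, depending on platelet counts", and those doses rise with platelets. They are starting doses, from which this trial departs on purpose, so the Weeks 12-16 inversion is an oddity of the titration rather than a breach of the label bands.

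**Conclusion.** Wrong as written; severity minor to moderate. For a patient who stays above 200 x 10^9/L without a 50% spleen reduction, the text of 6.2.3 omits the 15 mg BID step that Section 2.1 and the fourth bullet of 6.2.3 describe. It replaces that step with four more weeks at 10 mg BID followed by a one-step doubling.

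The cost is 20 against 30 mg/day in Weeks 12-16 compared with a patient at 100-200, and a 9% lower mean dose over Weeks 12-24 than the described titration. These figures rest on constant platelets, all targeted increases taken and no use of 25 mg BID. Patients with a 50% reduction may stay on their dose legitimately, and a patient whose count falls into the 100-200 range comes under the 15 mg BID rule.

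The documents do not give the share of patients above 200 at Week 12, so the number affected is unknown. A reader might infer an effect on the Week 24 response rate or on the early hemoglobin fall. Nothing in the documents quantifies either, and none is claimed. The sample size of 50, the 13-responder threshold and the operating characteristics do not depend on this rule.

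**What to change.** First compare the text with Figure 6-1. Then:

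- state the Week 12 rule, and with it the Week 16 catch-up, as platelets of at least 100 x 10^9/L with no upper limit for the 10 to 15 mg BID step;
- state that the 20 mg BID step from Week 16, at 200 x 10^9/L or more, applies to patients already on 15 mg BID.

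If a direct 10 to 20 mg BID step above 200 is intended, say so explicitly and amend the fourth bullet, with a reason for exceeding the label increment.

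The cost is a protocol amendment or a clarification letter to sites. No extra patients, visits or data are needed, and the statistical analysis does not change.
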